#### 7.8. Data Safety Monitoring Committee(DSMB)

This clinical trial will be monitored by a Data and Safety Monitoring Board (DSMB) which will comprise the following members:

A physician, a clinical pharmacologist, hepatologist, and a statistician, The DSMB will meet bimonthly.

The DSMB will review and evaluate the data on clinical safety collected during the study and assesses reports on serious adverse events and adverse events. DSMB will meet every month to review and evaluate safety data and to give recommendations based on the evaluation.

#### **Responsibilities of DSMB**

- 1. Provide independent, sound, and timely review of clinical trial safety data.
- 2. Advice investigators on whether to continue, modify or stop the clinical trial for safety or ethical reasons.
- 3. Safeguard the interests of the study participants.
- 4. Oversee the timely analysis, review, and publication of the results.
- 5. Ensure ongoing scientific validity, integrity, and clinical and scientific relevance of the study.

#### 7.9. Seeking clarifications

The participants will be told that they will have the opportunity to seek clarifications and to register complaints at any stage of the study. Study participants will be provided with contact details of two investigators (one of whom is the principal investigator), and the ERC for immediate contact (in case of an emergency) during the course of the study or to seek clarifications or register any complaints.

28.02.2025

## 8. Budget

Category	Total (LKR)
1. Participant Costs	60,000
2. Study Medications	1,091,000
3. Equipment & Supplies	30,000
4. Ethics & Administrative Costs	35,000
Subtotal	1,216,000
7. Contingency (10%)	121,600
Grand Total	1,337,600

## 8.1. Source of funding

Funding for the clinical trial will be provided with the personal funds of [name] and [name].

28.02.2025

## 9. Timeline

Activity	February	March	April	May	June	July	August	September	October	November	December
	2025	2025	2025	2025	2025	2025	2025	2025	2025	2025	2025
Literature											
survey											
Proposal											
Writing											
Ethics											
Clearance											
Participant											
Recruitment											
Randomization											
Intervention											
Follow up											
Data Analysis											
Report											
Writing											

28.02.2025

## 11. Annexures

11.7. Annexure 1C	
Case Report Form	
Participant ID:	Visit Date:
Participant Random Number:	
Review No: □	
History:	
Introduction:	
• Age:	
• Gender:	
Marital Status:	
Occupation:  Systemia Poviany	
Systemic Review:	
• CVS:	
• RS:	
• Nervous:	
• Gastrointestinal:	
• Gastronnestmar.	
Genitourinary:	
Musculoskeletal:	

1.

2.

3. Past Medical/S History:	urgical		
4. Drug			
History:			
5. Family			
History:			
6. Allergic			
_			
7. Social			
History:			
Alcohol:	None: □	Moderate: □	Heavy: □
Smoking:	None: □	Moderate:□	Heavv: □

28.02.2025

# **Examination:**

General examination:	
Height(cm):	
Weight(kg):	
Waist Circumference(cm):	
BMI:	
Other	
Findings:	
CVS examination:	
Blood Pressure(mmhg):	
Heart Rate:	
Other	
Findings:	
Respiratory Examination:	
Respiratory rate:	
Other	
Findings	
rinanigs.	
Findings:	
rindings	
rindings	
Abdomen Examination:	

Randomized, Quadruple-blind, Placebo-controlled, Clinical Trial to determine the effects of Coffee (caffeine
supplementation on Hepatic Steatosis and Fibrosis in Metabolic dysfunction-associated Steatotic Live
Disease(MASLD)Version 1

Other Important		
Findings:		

e	estigations:	
	FBC:	
	Serum Electrolytes:	
er.	r Assessments:	
	AST (IU/L):	
	ALT (IU/L):	
	GGT (IU/L):	
	Total Bilirubin:	
	CAP Score:	
	LSM (Fibro scan):	
	FIB-4 Score:	
	US scan	
	Findings:	
	E'I	
	Fibro scan	
	Findings:	
ab	abolic Assessments:	
	Profile:	
	• Total Cholesterol (mg/dL):	
	Triglycerides (mg/dL):	
	• HDL (mg/dL):	
	• LDL (mg/dL):	

Blood glucose:	
•	Fasting Blood Sugar (FBS) (mg/dL): HbA1c (%): Fasting Serum Insulin:
Others:	rasting Serum hisumi.
•	Serum Creatinine: UFR:

28.02.2025

## **Adherence to Intervention:**

## **Degree of adherence to Treatment:**

Over	the	nast	m	onth
OVEL	uic	Dast	1111	onui.

o ver the past me	,			
• Tablet:				
No	Poor	Moderate	Good	Complete
adherence □	adherence□	adherence□	adherence□	adherence□
• Diet:				
No	Poor	Moderate	Good	Complete
adherence □	adherence□	adherence□	adherence□	adherence□
Alcohol and	l Smoking intervent	ion:		
No	Poor	Moderate	Good	Complete
adherence □	adherence□	adherence□	adherence□	adherence□
Reason for Non	Adherence:			

## Followed treatment

- 0–6 days  $\rightarrow$  No adherence
- 7–13 days  $\rightarrow$  Poor adherence
- 14–20 days → Moderate adherence
- 21–27 days  $\rightarrow$  Good adherence
- 28 days (Every day) → Complete adherence

Adverse Events (AE) R	eporting:				
• Any AE observed?	☐ Yes		□ No		
• If yes,					
1. Degree:					
Mild: □	Moderate: □		Severe: □		
2. Relation to treat					
Non	Unlikely:	Possible:	Probable:		
Related: □					
3. Outcome:					
Recovered/resolved: □	Recovered/resolved: □				
Recovered/resolved with	Recovered/resolved with sequelae: □				
Fatal/Life threatening: □	Fatal/Life threatening: □				
Unknown: □					
4. Action Taken:					
No action□	Medical				
Discontinued□	Intervention□ Discontinued□				

Reported: □			
Summary of the event	t :		

28.02.2025

## 11.8. Annexure 1D.

# **Patient Identification Form.**

Parti	icipant ID:
Parti	icipant Random Number:
1.	Name:
2.	Gender: □ Male □ Female
3.	Age:
4.	Ethnicity:
5.	Occupation:
6.	Contact Number:
	Home:
	Office:
	Mobile:

Randomized, Quadruple-blind, Placebo-controlled, Clinical Trial to determine the effects of Coffee (caffeine)
supplementation on Hepatic Steatosis and Fibrosis in Metabolic dysfunction-associated Steatotic Liver
Disease(MASLD)Version 1.

7.	Address:			

28.02.2025

# 11.9. Annexure 1E

**Contact Number:** [name]

Patient Information Card	
Participant Name:	
Study Title: Randomized, Quadruple-blind, Pla the effects of Coffee (caffeine) supplementation Metabolic dysfunction-associated Steatotic Live	on Hepatic Steatosis and Fibrosis in
Investigational Product: Caffeine 400mg	
Trial Start Date:	End Date:
Contact Information	
Principal Investigator:	Investigator:
[name]	[name]
Institution: Faculty of Medicine, University of Kelaniya	Institution: Faculty of Medicine, University of Kelaniya
Address: [name]	Address: [name]

IMPORTANT INFORMATION: This individual is a participant in a clinical research study. If medical attention is required, please contact the principal investigator at the number listed above before administering treatment. In case of emergencies, follow standard medical procedures and notify the study team as soon as possible.

**Contact number:**[name]

For Healthcare Providers: Please be aware that this participant may be under specific study-related restrictions. For further information, contact the principal investigator.

In case of loss, please report to the study team immediately.

28.02.2025

# 11.10. Annexure 1F

# **Front Label**

# **Participant ID:**

**Random Number:** 

Contents: 60 capsules (200mg each)

**Ingredients:**Caffiene anhydrous

Suggested use: Take two capsules daily after dinner

This recommended dose of this product contains as much caffeine as 4 cups of coffee. Do not consume more than 400 mg of caffeine from any source in a 24 hour period. It may cause nervousness, irritability, sleeplessness and occasional rapid heart rates. In case of accidental overdose, seek professional assistance or contact a poison control center immediately

Storage: Store in a cool, dry place away from sunlight

Warnings: Keep out of reach of children. Do not use if the seal is broken.

Manufactured by: Nutricost

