## 4.7. Randomization, blinding and code breaking

This is a Quadruple-blind study and either the Participant, Care Provider, Investigator, Outcomes Assessor will be aware of treatment assignments prior to the final database locks at the conclusion of the study.

Computer-generated random numbers will be used for randomization. Both caffeine tablets and placebo tablets will be packed into identical white HDPE (High Density Polyethylene) plastic bottles numbered from 1 to 110 by a pharmacist or an independent third party. according to the list of computer-generated random numbers. After packing each bottle according to this list with either Caffeine tablets or placebo tablets, the list will be placed in a sealed envelope until completion of the trial. The label of each bottle will indicate only the patient's random number and the direction

28.02.2025

for taking the tablets. This number will be clearly noted on each patient's CRF forms and tablets would be provided hence.

The caffeine and placebo tablets will be manufactured in identical shape and size and will be film coated to give the same appearance.

Bottles containing 60 caffeine tablets will be issued on day of allocation and will contain medication required for 30 days. The packed and sealed bottles will be stored at the University of Kelaniya, Faculty of Medicine, under recommended storage conditions specified by the manufacturer and kept under lock and key and released in small batches to be given to patients. Therefore, all investigators and patients will be blinded.

The codes can be accessed any time and in the event of a Serious Adverse Effect(SAE) or a Serious Adverse Reaction(SAR) the code of that patient will be broken. All eligible participants are randomly assigned to the two groups according to patient recruitment order.

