#### 7.2. Outcome

The outcome of the adverse event will be classified according to the following definitions:

**Recovered / resolved:** the event has resolved (no further symptoms are present, and no treatment is being received by the subject).

Recovered / resolved with sequelae: the event has resolved but lingering effects may be present.

**Fatal** / **life threatening:** the subject died as a result of the event. This code should only be used for the event that caused the death, not any event that was present at the time of the subject's death.

28.02.2025

**Unknown:** will be used in the event that the subject is lost to follow-up and no reliable data can be obtained.

All observed AEs will be reported as described in the following sections.

Medically qualified investigators will obtain appropriate information to determine the outcome of the AE and to assess whether it meets the criteria for classification as a Suspected Unexpected Serious Adverse Reaction (SUSAR) requiring immediate notification.

The codes can be accessed all 24hrs and in the event of a SAE when the code of that patient will be broken.

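### The bottle label in Annexure 1F contradicts section 4.7, and the list custody conflicts with the code-break rule, so the blind is not secured as written

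*Protocol*

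**What the plan says.** **Label.** Protocol section 4.7 sets the rule: "The label of each bottle will indicate only the patient's random number and the direction" for taking the tablets. The same section describes matching bottles numbered 1 to 110, and caffeine and placebo tablets film-coated to look alike. Annexure 1F, the only label in the List of Annexures, goes further. Its front panel states "Contents: 60 capsules (200mg each", gives the ingredient as "Caffiene anhydrous", directs "Suggested use: Take two capsules daily after dinner" and adds "This recommended dose of this product contains as much caffeine as 4 cups of coffee", followed by a list of caffeine effects. Section 5 says the placebo is made from starch. No placebo label and no arm-neutral wording appear.

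**Card.** The patient card in Annexure 1E reads "Investigational Product: Caffeine 400mg".

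**Code break.** After packing, section 4.7 says, "the list will be placed in a sealed envelope until completion of the trial". It then says that the codes can be reached at any time and that a patient's code is broken on a serious adverse event or serious adverse reaction. Section 7.2 repeats the round-the-clock access and the break "in the event of a SAE when the code of that patient will be broken". Section 4.7 also commits to keeping four roles unaware of assignment until database lock (it prints 'either', evidently for 'neither').

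**The concern.** Section 4.7 and Annexure 1F cannot both be followed: a label limited to a number and directions cannot also state an ingredient, a strength and caffeine warnings. Nor can a list stay sealed to the end of the trial if it is also what is opened whenever a code is needed, and nothing else is described for that purpose.

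The blind matters here because several inputs to the results depend on behaviour or judgement. Participants carry out their own diet and exercise changes (sections 5.2 and 5.3). Adverse-event causality rests on the investigator's opinion (section 7.1), and that rating feeds one of the dosing-stop criteria in section 7.7. Section 3.1 justifies the placebo by the need to control psychological effects and bias. If participants or staff could infer the arm, each of these could shift differently between the groups.

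**Working it through.** No power or effect calculation applies. The check is whether the passages agree, and how many participants each reading touches.

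**Step 1: quantities.** The label gives 60 units of 200 mg, two per day.
- Supply: 60 / 2 = 30 days. Section 4.7 says a bottle of 60 lasts 30 days. Agrees.
- Daily amount: 2 × 200 mg = 400 mg. The card in Annexure 1E says 400 mg. Agrees.

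The conflict is therefore about what the label discloses and what dosage form it names, not about amounts.

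**Step 2: content side by side.**

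| Item | Section 4.7 | Annexure 1F |
|---|---|---|
| Random number | yes | yes |
| Directions | yes | yes |
| Ingredient | excluded by 'only' | caffeine anhydrous |
| Strength | excluded by 'only' | 200 mg |
| Caffeine warnings | excluded by 'only' | present |
| Dosage form | film-coated tablets | capsules |

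**Step 3: the two ways of using Annexure 1F.** Section 4.4 gives 55 per group and 55 + 55 = 110 in total.
- *Caffeine bottles only.* The label identifies caffeine, and its absence identifies placebo. All 110 allocations can be read from the bottle, including by staff who count returned tablets each month (section 5). The label also sets a ceiling of 400 mg of caffeine from all sources in 24 hours. The labelled daily amount is already 400 mg, so 400 − 400 = 0 mg is left for coffee. Read in one arm only, that could change coffee intake in that arm alone.
- *All bottles.* The label does not distinguish the arms. The 55 bottle numbers assigned to placebo carry an ingredient and strength that are untrue of a starch product.

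The protocol states neither use.

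**Step 4: custody of the codes.** Section 4.7 describes one list covering bottles 1 to 110, in one envelope. Sections 4.7 and 7.2 speak of breaking the code of the affected patient, which implies a one-person disclosure. No individual envelope, other single-participant device or code holder is named. If the full list were opened to whoever needs one code, 110 − 1 = 109 other allocations would be visible. If an independent person looked up one line, none need be. The text does not settle which happens. The random number is on each case report form (Annexure 1C) together with the scan results and adverse-event causality, so anyone who had seen the list could link it to outcomes.

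**The case against.** Three stronger readings are tempting, and the documents do not support them.

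1. A reader might infer that the label unblinds the whole trial. That follows only if Annexure 1F goes on caffeine bottles alone. No passage says so, and a single template with matching bottles and tablets makes a common label at least as natural a reading. With a common label, any expectation it creates is the same in both arms, and neither differential behaviour nor biased causality ratings follow from it.
2. A reader might infer that the first serious adverse event exposes every allocation. The protocol never says that the sealed list is the code-break tool, and it refers to the code of one patient. Packing is given to a pharmacist or independent third party, who could look up one entry without showing the rest. Exposure of other codes is possible, not stated.
3. A reader might take the patient card as evidence of unblinding. It is the same for every participant, it prints the trial title, which says the study is placebo-controlled, and section 4.7 governs bottle labels, not cards. The card needs arm-neutral wording for accuracy, no more.

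It also cannot be said what participants are told overall about placebo, because the information sheets and consent forms are not available for this review. The capsule/tablet difference may be only a slip in wording, since count and strength agree.

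These points limit the size of the claim. They leave the two contradictions standing: label rule against label template, and sealed list against access at any time. Neither branch of label use is acceptable as it stands.

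**Conclusion.** The concern holds in this limited form: the blind is not secured as written. Annexure 1F contradicts section 4.7 on label content and dosage form. Depending on a use that the protocol leaves open, it would either reveal the arm of all 110 participants or put a false content statement on the bottles of 55. The custody and code-break provisions contradict each other, and without a described single-participant break, up to 109 other allocations could be seen when one is opened. The figures assume equal groups of 55, as section 4.4 states. The 110 is conditional on caffeine-only labelling, and the 109 on the full list being used for the break.

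The label contradiction is certain from the text. The code-break exposure is an inference from silence and is less certain. No sample size, power or analysis result changes. It should nevertheless be settled before any bottle is dispensed, because a lost blind cannot be restored at analysis.

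**What to change.** Reconcile sections 4.7 and 7.2 with Annexure 1F:

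- **Label.** Put one identical, arm-neutral label on every bottle: 'caffeine or placebo', random number, directions and the trial-use warning. Amend section 4.7 to list exactly these items, since its present wording would exclude a contents line. Any caffeine warning that the investigators keep should be worded conditionally and printed on all bottles.
- **Card.** Word Annexure 1E the same way.
- **Dosage form.** Use one term throughout, matching the product actually supplied, and confirm that the matched-appearance statement in section 4.7 applies to it.
- **Code break.** State who holds the codes, independently of the investigators. State that a break reveals one participant only (individual sealed envelopes are one way; any equivalent device would do), that it is logged, and that the result is withheld from the Fibroscan operator and the analysts. Reword the sealed-list sentence so that it no longer conflicts with access at any time. The clinical trigger for a break is for the investigators to settle and to state consistently in sections 4.7 and 7.2.

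The cost is reprinting the label and card, preparing the single-participant code records, and a short amendment. Sample size and analysis are unaffected.

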# **Back Label**

This medication is part of a clinical trial. Do not share with others. If you experience any adverse effects, contact the study team immediately.

28.02.2025

